12.4	Event Reporting	21
13.	Early Termination.....	21
14.	Data Analysis.....	21
14.1	General Considerations	21
14.2	Analysis Population	21
14.3	Safety Population.....	22
14.4	Demographics	22
14.5	Primary Outcome Evaluation	22
14.6	Secondary Outcomes Evaluation.....	23
14.7	Primary Safety Evaluation	23
14.8	Sample Size	23
15.	Study Administration.....	24
15.1	GCP Statement.....	24
15.2	Informed Consent	24
15.3	Institutional Review Board	24
15.4	Sponsor Monitoring.....	25
15.5	Documentation and Intended Use of Data	25
15.6	Record Retention.....	25
16.	References	26
	Appendix 1 – Bland-Altman LOA Meta-Analysis	27

1. Protocol Synopsis

Name of Sponsor: Tatch, Inc.	
Protocol Number:	TCH-110
Protocol Title:	A Multi Center, Single Arm, Quantitative Study Assessing Performance of TatchSleep Pro as a Tool to Aid in Sleep Apnea Diagnosis
Investigational Device:	TatchSleep Pro
Study Centers:	Approximately 3
Study Objectives:	
Primary Objectives:
 
• Demonstrate clinical agreement between TatchSleep Pro and PSG signals by comparing the Apnea Hypopnea Index (AHI) values derived from a clinical reading of each set of signals. 
Secondary Objectives:
 
• Compare TatchSleep Pro and PSG signals across different positions and in the presence of motion.• Evaluate the reliability of TatchSleep Pro signals across readers.
Endpoints:	
Primary Effectiveness Endpoints:
 
• Agreement between the AHI as determined by TatchSleep Pro and PSG signals as measured by the Pearson correlation.• Bland-Altman 95% limits of agreement for TatchSleep Pro and PSG AHI 
Secondary Effectiveness Endpoints:
 
• Deming regression parameters estimated by weighted regression of TatchSleep Pro AHI on PSG AHI.• Estimation of the inter-rater reliability for TatchSleep Pro AHI.• Estimation of the agreement between diagnoses of mild, moderate and severe sleep apnea based on TatchSleep Pro and PSG AHI.

	
 • Estimation of the Bland-Altman 95% limits of agreement of TatchSleep Pro and PSG AHI by position (supine v. non-supine). 
Primary Safety Endpoints:
 
 • Incidence of Adverse Events (AEs) and Serious Adverse Events (SAEs) related to the device throughout the study period.
Study Design:	
This is a multi-center, single-arm, quantitative study evaluating the effectiveness of the TatchSleep Pro wireless sensors as a tool to aid in sleep apnea diagnosis as compared to an overnight PSG evaluation.
 
Investigators will identify approximately 50 eligible patients who have been recommended to receive an overnight PSG for the detection/evaluation of sleep apnea. After informed consent is obtained, a brief sleep-related medical history will be collected including relevant demographics. Females of childbearing potential will be asked to undergo a urine dipstick pregnancy test to determine their eligibility for inclusion in the study.
 
Patients will undergo their PSG test while simultaneously wearing 2 TatchSleep Pro patches and an FDA-cleared pulse oximeter compatible with and connected to the TatchSleep Pro system for a single night at the clinic. The same make and model of pulse oximeter will be used for all subjects. Patients will be observed overnight by trained sleep technicians who will setup the TatchSleep Pro device and collect the sleep data via the companion smartphone application.
 
A follow-up communication will be made with patients within 5 days after the sleep study to assess any adverse events.
 
Following the data collection, sleep data from PSG and TatchSleep Pro will be scored by an independent qualified sleep technologist (the primary reader) to yield an analysis of the accuracy of TatchSleep Pro compared with the PSG signals. At least one and up to two additional readers (secondary readers) will score only the TatchSleep Pro data to obtain an estimate of inter-rater reliability.

Study Device:	TatchSleep Pro paired with the same make and model of compatible FDA cleared pulse oximeter for all subjects
Eligibility Criteria:	
Inclusion Criteria:
 
 1. Be at least 21 years of age.

	
2. Have a referral to the study site from a physician to complete an overnight polysomnogram test for sleep apnea detection or follow-up.
 
3. Be willing and able to wear two TatchSleep Pro patches and an FDA-cleared pulse oximeter in conjunction with a polysomnogram, for a single night.
 
4. Be able and voluntarily willing to sign a written informed consent form prior to the initiation of any study procedures. Adult patients unable to provide written informed consent on their own behalf will not be eligible for the study.
 
Exclusion Criteria:
 
 1. Women who are pregnant, trying to get pregnant or who have a positive urine pregnancy test on the day of the study. 2. Women who are breast-feeding 3. Significant cardiorespiratory disease 4. Potential respiratory muscle weakness due to neuromuscular condition 5. Awake hypoventilation or suspicion of sleep related hypoventilation 6. Chronic opioid medication use 7. History of stroke 8. History of severe insomnia 9. Any known health condition that, in the opinion of the Investigator, would exclude the patient from participating in the study.
Number of Patients:	Approximately 50
Data Elements:	
The following data elements will be collected:
 
 • Height, weight, age, gender, skin tone (according to the Fitzpatrick scale), presence or lack of body hair under TatchSleep Pro patches. • TatchSleep Pro data (including patient movement, sleep position, pulse oximetry, and respiration) • PSG data (including sleep stages, total sleep time, sleep position, pulse oximetry, heart rate, and respiration). • Adverse events
Statistical Methods:	
Accuracy of the TatchSleep Pro device will be demonstrated by comparing the Pearson correlation of TatchSleep Pro and PSG AHI to a performance goal. The performance goal is based on a meta-analysis of FDA-cleared similar devices. Fisher's transformation and one-sided Z-test will be used to test the hypotheses with a significance level of 0.025. The upper and lower 95% Bland-Altman limits of agreement will be calculated and statistically compared using a Wald test to performance goals based on a meta-analysis of FDA-cleared similar devices.

	Deming regression will also be presented. The inter-rater reliability of TatchSleep Pro AHIs will be calculated.
--	--

CONFIDENTIAL

2. Background and Rationale

Obstructive sleep apnea (OSA) is characterized by reduced breathing and breathing cessation during sleep. It is a highly prevalent condition that affects an estimated 14% of adult men and 5% of adult women aged 30 to 70 [1]. OSA is associated with more than 30 chronic conditions, such as increased risk of cardiovascular complications, and daytime fatigue and sleepiness. While the clinical gold standard for the diagnosis of OSA is polysomnography, these in-laboratory tests are expensive, time consuming, and labor intensive.

In recent years there is a growing use of home sleep tests (HSTs) as a more convenient and cost-effective alternative to diagnose sleep disorders. Nevertheless, HSTs currently on the market contain several complex wires and tubes that may make it difficult for patients to use on their own. In addition, patients report that they can be intrusive and uncomfortable. These factors lead to unreliable data collection and ineffective diagnosis of OSA [2].

TatchSleep Pro is a system comprised of flexible, thin, and wireless adhesive patches, coupled with an FDA-cleared compatible pulse oximeter, for the detection of sleep apnea. The wearable sensors detect various physiological parameters related to sleep quality, including respiration, SpO₂, and sleep position, and transmits data wirelessly to a smartphone app in real time. The data recorded by the patches is relayed to remote secure storage, from where it is downloaded to a local PC. The study output file is prepared by Tatch staff for review by a qualified sleep scorer.

The TatchSleep Pro device was bench-tested against industry standard polysomnography devices to compare the different sensors. Using its proprietary technology, TatchSleep Pro showed excellent accuracy and sensitivity in measuring respiration and sleep position. Previous feasibility testing was conducted on approximately 30 patients to evaluate the user experience and effectiveness in using the patch technology.

As a low-cost and user-friendly home sleep testing system, TatchSleep Pro has the potential to improve the detection of OSA while reducing the burden on patients and providers caused by complicated and invasive sleep kits.

In the current study, TatchSleep Pro will be evaluated as a tool to assist physicians in determining the overall Apnea Hypopnea Index (AHI) of a patient. Tatch, Inc. has partnered with the multiple clinical sites for this study.

3. Study Objectives

3.1 Primary Objective

- Demonstrate clinical agreement between TatchSleep Pro and PSG signals by comparing the Apnea Hypopnea Index (AHI) values derived from a clinical reading of each set of signals.

3.2 Secondary Objectives

- Compare TatchSleep Pro and PSG signals across different positions and in the presence of motion.
- Evaluate the reliability of TatchSleep Pro signals across readers.

4. Study Endpoints

To support the study's objectives, the following endpoints will be calculated:

Primary Effectiveness Endpoints:

- Agreement between the AHI as determined by TatchSleep Pro and PSG signals as measured by the Pearson correlation.
- Bland-Altman 95% limits of agreement for TatchSleep Pro and PSG AHI

Secondary Effectiveness Endpoints:

- Deming regression parameters estimated by weighted regression of TatchSleep Pro AHI on PSG AHI.
- Estimation of the inter-rater reliability for TatchSleep Pro AHI.
- Estimation of the agreement between diagnoses of mild, moderate and severe sleep apnea based on TatchSleep Pro and PSG AHI.
- Estimation of the Bland-Altman 95% limits of agreement of TatchSleep Pro and PSG AHI by position (supine v. non-supine).

Primary Safety Endpoint

- Incidence of adverse events and serious adverse events (SAEs) related to the device throughout the study period.

5. Study Overview

This is a multi-center, single-arm, quantitative study evaluating the effectiveness of the TatchSleep Pro wireless sensors as a tool to aid in sleep apnea diagnosis as compared to an overnight PSG evaluation. This study is intended to evaluate the performance of the TatchSleep Pro against PSG for the target population.

Investigators will identify approximately 50 eligible patients who have been recommended to receive an overnight PSG for the detection/evaluation of sleep apnea. After informed consent is obtained, a brief medical history will be collected including relevant demographics. Females of childbearing potential will be asked to undergo a urine dipstick pregnancy test to determine eligibility for study participation.

Patients will undergo their PSG test while simultaneously wearing 2 TatchSleep Pro patches and a paired FDA-cleared compatible pulse oximeter for a single night at the clinic. The same make and model of pulse oximeter will be used for all subjects. Patients will be observed overnight by trained sleep technicians who will setup the TatchSleep Pro device and will record the sleep data via the companion smartphone application.

A follow-up phone communication will be made with patients within 5 days after the sleep study to assess any adverse events.

TABLE 1: SCHEDULE OF ASSESSMENTS

Procedure or Assessment	Study visit			
	(Day -7 to Day 1) - Screening	Day 1 - Night	Day 2 - Morning	Day 3-7 follow-up
Informed Consent	X			
Eligibility Assessment	X			
Urine Pregnancy Test		X		
Polysomnogram (PSG)		X		
Administer TatchSleep Pro		X		
Adverse Event Assessment		X	X	
Follow-up Communication				X

6. Study Population

Approximately 50 participants at least 18 years of age will be enrolled in this study. These patients will be identified by a clinician to complete an overnight PSG test for sleep apnea detection or follow-up.

6.1 Inclusion Criteria

Eligible participants must meet all of the following criteria:

1. Be at least 21 years of age.
2. Have a referral to the study site from a physician to complete an overnight PSG test for sleep apnea detection or follow-up.
3. Be willing and able to wear two TatchSleep Pro patches and an FDA-cleared pulse oximeter in conjunction with a PSG, for a single night.
4. Be able and voluntarily willing to sign a written informed consent form prior to the initiation of any study procedures. Adult patients unable to provide written informed consent on their own behalf will not be eligible for the study.

6.2 Exclusion Criteria

Participants in the study must not meet any of the following criteria:

1. Women who are pregnant, trying to get pregnant or who have a positive urine pregnancy test on the day of the study.
2. Women who are breast-feeding.
3. Significant cardiorespiratory disease
4. Potential respiratory muscle weakness due to neuromuscular condition
5. Awake hypoventilation or suspicion of sleep related hypoventilation
6. Chronic opioid medication use
7. History of stroke
8. History of severe insomnia
9. Any known health condition that, in the opinion of the Investigator, would exclude the patient from participating in the study.

7. Patient Recruitment

Approximately 50 patients will be enrolled across 3 clinical sites. Potential patients who have been recommended to receive an overnight PSG for the detection/evaluation of sleep will be approached by key study personnel to discuss the study. Some of those patients might be referrals from fellow clinical sites or other healthcare providers that may or may not be aware of the study.

8. Study Procedures and Assessments

8.1 Eligibility Assessment and Informed Consent

An informed consent form (ICF) must be signed by prospective patients prior to initiating any study-specific procedures.

The Investigator or designee will confirm that the patient meets all inclusion and no exclusion criteria.

The patient must sign a written ICF prior to the initiation of any study procedures. The enrolled subject will be given a signed copy of the ICF to take home. Adult subjects unable to provide written informed consent on their own behalf will not be eligible for the study.

The ICF and any other written information provided to the patients will be revised whenever important new information becomes available that may be relevant to the patient's consent, or if there is an amendment to the protocol which necessitates a change to the content of the patient's informed consent. Any written ICF and written information must receive approval by the IRB in advance of use. Only the most up to date IRB-approved ICF must be used to consent new patients.

8.2 Urine Pregnancy Test

Females of childbearing potential will be asked to undergo a urine dipstick pregnancy test on Day 1 in order to rule out pregnancy prior to starting the study.

8.3 Complete Patient Case Report Form (CRF)

CRFs will be provided for the recording of data. The Investigator or designee will record data from all observations and assessments specified in the protocol, including demographics, physical attributes and adverse events on the CRFs provided by the Sponsor.

8.4 Polysomnography

Patients will be hooked up to a PSG on Day 1 (Night) according to the standard of care at the clinical site. This will record brain waves, blood oxygen level, heart rate and breathing, as well as eye and leg movements.

8.5 TatchSleep Pro Administration

The TatchSleep Pro will be connected to the patient by the investigator or designee according to the instructions in the provided User Manual. The investigator or designee will follow the instructions in the pre-loaded smartphone app to place the patches on the patient's chest and abdomen, as well as the pulse oximeter on the patient's finger. Once the sensors are set up and the participant is ready for bed, the investigator or designee will start the data collection using the app.

Details about TatchSleep Pro management can be found in Protocol Section 11.

8.6 Follow-up Communication

A follow-up communication (email or phone call) will be made with patients within 5 days after the sleep study to check in on how they are doing and follow-up on any adverse events. If after three documented attempts the patient could not be reached for feedback, the patient will be considered as "lost to follow-up".

8.7 Onsite PSG Study Scoring and Export

After the completion of data collection from patients, de-identified PSG signals will be exported from the PSG at the clinical site including, at a minimum, manual position annotations and sleep staging scored according to the standard of care by a sleep technologist at the study site. Raw PSG sleep data (including, at a minimum, respiratory effort, respiratory pressure, respiratory flow and oxygen saturation signals) will be extracted and presented to qualified readers as described below.

9. Study Scoring

Once study enrollment and all sleep tests are complete, and all exported PSG data (with position annotations and sleep staging) has been received by the Sponsor, the primary reader will score all sleep study recordings made simultaneously with TatchSleep Pro and the PSG device from all sites. The primary reader will be blinded to the device used to collect the data under review as well as any information which may allow them to link the two studies from each patient. The AHI will be calculated for each study, and the set of AHIs derived from TatchSleep Pro data will be compared with those derived from PSG data using Pearson correlation to demonstrate accuracy (see Protocol Section 11 for more details). At least one and up to two additional readers (secondary readers) will each score all sleep study recordings made using the TatchSleep Pro device at all sites. The AHIs derived from these scorings will be used to calculate the inter-rater reliability for the TatchSleep Pro device signals.

9.1 Scoring Population

Studies of subjects whose TatchSleep Pro recording does not encompass the sleep period indicated by PSG will not be scored [3]. Studies from all other participants who are enrolled, meet all the inclusion criteria and none of the exclusion criteria, and whose PSG study has >4 hours of sleep duration will be scored [3].

9.2 Reasons for Data Exclusion

Time periods marked by the reader as "Movement" or "Artifact" (collectively referred to as "invalid") in a study will not contribute to the total sleep time for the purpose of calculating AHI for that study (per guidelines in the American Academy of Sleep Medicine (AASM) Manual for the Scoring of Sleep and Associated Events section IX: Home Sleep Apnea Testing Rules for Adults). Percentage of "invalid" time will be reported for each study.

9.3 Blinding

All studies will be presented on the same viewing and scoring platform. The readers will be blinded to patient identification and the data collection device for each study. Specifically:

- All data presented to the reader will be fully anonymized and will not include any information which could allow the reader to link a subject's two data sets. All Protected Health Information (PHI), ID numbers, and study meta-data such as time

and date will be removed.

- The reader will review patient studies in a predetermined randomized order such that sequential readings of data from the same patient will be avoided.
- All studies will be reviewed using the same analysis software, and using identical, system-agnostic signal labeling (eg, "Flow" will be used to label both the TatchSleep Pro TATCH-SUM-FLOW and the PSG Airflow waveforms).

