9.4 Scoring Procedure

Readers will be asked to score studies using the provided viewing software as they normally would in a clinical setting and in accordance with the AASM Manual for the Scoring of Sleep and Associated Events. Hypopneas will be scored using the recommended rule 1A criterion as laid out in the AASM (v2.6), Chapter VIII Respiratory Rules Part 1: Rules for Adults, Section D: Scoring of Hypopneas.

The same data channels will be presented to the reader in the same order and with the same labelling for every study, including:

- Abdominal respiratory effort, labelled "ABD" from either the PSG system or the TatchSleep Pro patches, as applicable
- Thorax respiratory effort, labelled "THX" from either the PSG system or the TatchSleep Pro patches as applicable
- Position channel, labelled "Position" from either the PSG system or the TatchSleep Pro patches, as applicable
- Air flow (PSG) or Tatch-Sum-Flow (TatchSleep Pro) as applicable, labelled "Flow"
- Nasal pressure (PSG) or Tatch-Sum-Pressure (TatchSleep Pro) as applicable, labelled "Pressure"
- Pulse oximetry-derived blood oxygen saturation (SpO₂), labelled "SpO₂" from either the PSG system or the TatchSleep Pro compatible pulse oximeter as applicable

On any of the respiratory signals, the reader will be able to mark:

- Apnea
- Hypopnea

On the SpO₂ signal, the reader will be able to mark:

- Relative desaturation

Additionally, the reader may mark any signal with the following signal quality indicators:

- Artifact
- Movement

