14.5 Primary Outcome Evaluation

The first co-primary performance objective is to demonstrate that the correlation between PSG and TATCH AHI is greater than the performance goal (PG) using a significance level of 0.025.

The hypotheses to be tested are:

$$H_0: \rho \leq PG \quad \text{versus} \quad H_a: \rho > PG$$

where ρ is the Pearson correlation between PSG and TatchSleep Pro AHI and PG is the performance goal. The performance goal is set to be 0.862, the lower 95% confidence limit for the correlation of RDI and AHI between PSG and Peripheral Arterial Tonometry (PAT) as calculated in a meta-analysis of 12 studies [5]. Fisher's transformation and one-sided Z-test will be used to test the hypotheses with a significance level of 0.025.

The second co-primary performance objective is to demonstrate that the 95% limits of agreement between PSG and TATCH AHI within the performance goals (PG_L and PG_U) using a significance level of 0.05.

The hypotheses to be tested are:

$$\begin{aligned} H_{01}: UL &\geq PG_U & \text{vs. } H_{a1}: UL < PG_U \\ H_{02}: LL &\leq PG_L & \text{vs. } H_{a2}: LL > PG_L \end{aligned}$$

where UL and LL are the upper and lower 95% limits of agreement between PSG and TATCH

AHI. The performance goals PG_U and PG_L are set to be the upper and lower limits, respectively, of the 95% confidence interval in a meta-analysis of 7 FDA approved devices (28.4 and -30.6). The full meta-analysis is detailed in Appendix 1. A Wald Z-test will be used to test the hypotheses with a significance level of 0.05. All three null hypotheses need to be rejected in order for the trial to be successful.

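### Section 9.3 keeps a patient's two same-night recordings from being read back to back but sets no other separation; two counterbalanced reading blocks would guard better against carry-over at little cost

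*Combined protocol and SAP*

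**What the plan says.** Section 9 (Study Scoring) gives both recordings to one person: "the primary reader will score all sleep study recordings made simultaneously with TatchSleep Pro and the PSG device from all sites". Reading begins "Once study enrollment and all sleep tests are complete" and the PSG exports have arrived, so both recordings of each patient sit in one pool from the start. One or two secondary readers score the TatchSleep Pro recordings only (Synopsis, Study Design; section 9).

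The plan has several safeguards:

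- Section 9: "The primary reader will be blinded to the device used to collect the data under review".
- Section 9.3: the material shown "will not include any information which could allow the reader to link a subject's two data sets". Identifiers, dates and times are stripped, and one software package is used for all studies.
- Section 9.4: "The same data channels will be presented to the reader in the same order and with the same labelling for every study".
- Section 9.3, on order: "The reader will review patient studies in a predetermined randomized order such that sequential readings of data from the same patient will be avoided".

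The last item is the only rule that separates a patient's two readings. The text supplied gives no minimum number of intervening studies, no time interval, no split into sessions, no locking of first readings and no analysis of reading order.

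**The concern.** The primary reading is in effect a crossover within one reader, with two recordings of the same night as the two periods. The safeguards remove labels and metadata. They do not remove content. Both systems are worn at the same time, and section 9.4 shows effort, position, flow, pressure and SpO₂ for each in the same layout. A night with unusual desaturations or posture changes could be recognised when it appears again.

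If recognition pulls the second scoring towards the first, the two reading errors for that patient become positively correlated. The TatchSleep Pro minus PSG difference then shrinks, the limits of agreement narrow and the Pearson correlation rises. All three null hypotheses in section 14.5 become easier to reject, so the bias runs in one direction only, towards the device.

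**Working it through.** **1. The plan's own figures (section 14.8).** Inputs: 46 subjects, assumed correlation 0.98, one-sided 0.025, and from section 14.5 "The performance goal is set to be 0.862, the lower 95% confidence limit for the correlation".

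- Fisher z: atanh(0.98) − atanh(0.862) = 2.2976 − 1.3011 = 0.9965.
- 0.9965 × √43 = 6.53, and 6.53 − 1.96 = 4.57. Power exceeds 99.99%, in line with the stated 99.99%.
- Limits of agreement: pilot bias = (10.6 − 3.2)/2 = 3.7. With SD 7.0 the limits are 3.7 ± 1.96 × 7.0 = 17.4 and −10.0.
- Standard error of a limit = √3 × 7.0/√46 = 1.79. Power exceeds 99.99% for both limits (stated 99.9%).

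No stated figure is in dispute.

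**2. How close the two readings can fall.** There are 46 patients and 92 positions. A gap of g positions can occur in 92 − g ways. With gap 1 barred, the total over g = 2 to 91 is 4,095. Treating all non-adjacent placements of one patient's pair as equally likely gives:

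| Gap between the two readings | Calculation | Expected patients of 46 |
|---|---|---|
| exactly 2 (one study between) | 46 × 90/4,095 | 1.0 |
| 5 or less | 46 × (90+89+88+87)/4,095 = 46 × 354/4,095 | 4.0 (9%) |
| 10 or less | 46 × (9 × 86)/4,095 = 46 × 774/4,095 | 8.7 (19%) |

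The mean gap is 31.7. The chance that at least one patient has a single study between readings is about 1 − e^(−1.01) = 64%. A simulation of 20,000 permitted orders gave 4.0, 8.7, 31.7 and 64%. With 50 patients the results are similar (8% within 5 positions, 17% within 10, mean gap about 34).

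**3. What carry-over would do.** The documents give no recognition rate and no reader error, so these inputs are assumptions: reader error SD 3 events/hour per reading, induced error correlation c = 0.2 to 0.5, and a share f of patients affected. I take f = 0.19 (those within 10 positions), with f = 1 as an extreme.

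- SD of differences = √(49 − 2 × 9 × c × f). For c = 0.5 and f = 0.19 this is √(49 − 1.71) = 6.88.
- Correlation, with equal AHI variances on the two devices. At a true value of 0.862 and difference variance 49, each AHI variance is 49/(2 × 0.138) = 177.5. The correlation becomes 0.862 + 9cf/177.5. For c = 0.5 and f = 0.19 this is 0.862 + 0.855/177.5 = 0.867.
- One-sided error at 0.862: (atanh(0.8668) − 1.3011) × √43 = 0.125, and Φ(0.125 − 1.96) = 3.3%.

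| f | c | SD of differences | Correlation (true 0.862) | One-sided error |
|---|---|---|---|---|
| 0 | – | 7.00 | 0.862 | 2.5% |
| 0.19 | 0.2 | 6.95 | 0.864 | 2.8% |
| 0.19 | 0.5 | 6.88 | 0.867 | 3.3% |
| 1 | 0.2 | 6.74 | 0.872 | 4.5% |
| 1 | 0.5 | 6.32 | 0.887 | 10.6% |

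**4. Effect on the limits of agreement.** At SD 6.88 the limits are 3.7 ± 1.96 × 6.88 = 17.2 and −9.8, against 17.4 and −10.0 without carry-over. The goals are 28.4 and −30.6. Without carry-over the one-sided 95% bound on the upper limit is 17.4 + 1.645 × 1.79 = 20.4, already well inside 28.4. Carry-over of this size does not decide that test.

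**5. At the planning correlation.** At 0.98 each AHI variance would be 49/(2 × 0.02) = 1,225, and the shift is 0.855/1,225 = 0.0007, which is negligible.

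**The case against.** The case on the other side is substantial.

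- **Other safeguards exist.** It would be wrong to read the order rule as the only protection. Anonymisation, metadata removal, random order and a device-neutral display all make recognition less likely. The signals also come from different hardware, with patch-derived flow and pressure in place of airflow and nasal pressure, and a separate oximeter. This stands: recognition is possible, but nothing in the documents shows that it will happen.
- **The task resists memory.** The reader marks individual events over a whole night, and the AHI is calculated afterwards. Recalling that a night was unusual does not fix the count. This stands as a reason to expect a small effect.
- **Most pairs are far apart.** About 81% of patients have readings more than 10 positions apart. This stands, but position is not time, and the plan sets no interval.
- **It could be checked.** A reader might infer that carry-over could never be detected afterwards. The documents do not support that. The order is predetermined, so the gap and the device read first can be known for every patient. The secondary readers score TatchSleep Pro without scoring any PSG, so their scores cannot carry PSG memory. What is missing is a stated plan to use this information.
- **Much larger inflation is tempting to infer.** If the whole second AHI were pulled halfway to the first, simulation at a true correlation of 0.862 puts the error of the correlation test at 5.7% with 10% of patients recognised and 9.9% with 20%, against 2.9% with none. That is a stronger mechanism with no support in the documents. It is a stress test, not an estimate.
- **Details may sit elsewhere.** Section 14.1 defers further details to a Statistical Analysis Plan. A spacing rule could be there, but none is in the text supplied.

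**Conclusion.** The point holds as a cheap improvement in design. The plan contains no error or contradiction here. One reader scores both same-night recordings from one pool, and only consecutive readings are barred. About 4 of 46 patients would then be read twice within 5 positions and about 9 within 10. The direction of any carry-over is certain given the mechanism (it favours the device), but its size is not known.

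Under the assumptions above (reader error SD 3, error correlation 0.5, in the 19% of patients within 10 positions), the SD of differences falls from 7.0 to about 6.9. The limits-of-agreement verdict does not move. The one-sided error of the correlation test rises from 2.5% to about 3.3%, and this matters only if the true correlation lies near 0.862. A reader might infer that both co-primary results are at risk. The documents do not support that for the limits of agreement, where the goals are wide, nor for the correlation if it is close to the planned 0.98.

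**What to change.** In section 9.3, replace the rule against consecutive readings, for the primary reader, with two reading blocks:

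- each block holds exactly one recording per patient;
- a random half of patients have TatchSleep Pro in block 1 and the other half have PSG;
- order is randomised within each block;
- a fixed washout separates the blocks, its length for the sponsor to choose (for example 2 weeks);
- block 1 scores are locked before block 2 is released.

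In section 14, add two sensitivity analyses that need no new data. First, compare the secondary readers' TatchSleep Pro AHI with the primary reader's PSG AHI. This comparison also contains between-reader variation, so somewhat wider limits are expected even without carry-over. Second, tabulate the differences by which device was read first.

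Cost: a different randomisation list, and primary scoring that finishes a few weeks later. No extra patient, reader or reading is needed, and the sample size and power are unchanged.
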